8 EFFICACY ASSESSMENT

8.1 Description of efficacy endpoints assessment parameters

The individual endpoints will be defined as follows.

8.1.1 Death

- **Any death:** death from any cause

"ACORES2" protocol, version 1-3 of 07/04/2020

- **CV death:** any death with a clear relationship to underlying coronary heart disease (including death secondary to acute MI, sudden death, unobserved and unexpected death, resuscitated out-of hospital cardiac arrest that does not survive to hospital discharge), stroke, and other death that cannot definitely be attributed to a non-CV cause.

8.1.2 Myocardial infarction

The definition of MI is based on the new Fourth Universal Definition of Myocardial Infarction written by Thygesen et al on behalf of the Joint ESC/American College of Cardiology Foundation (ACCF)/AHA/World Health Federation (WHF) Task Force for the Universal Definition of Myocardial Infarction (48).

ACORES-2 will consider only **spontaneous MI**, excluding MI type 3 (fatal), which will be captured separately as death.

MI Type 1: Spontaneous MI: Symptoms of myocardial ischemia, new ischemic changes, development of pathological Q waves, imaging evidence of new loss of viable myocardium or new regional wall motion abnormality in a pattern consistent with an ischaemic etiology, identification of a coronary thrombus by angiography or autopsy.

MI Type 2: Secondary MI: Symptoms of myocardial ischemia, new ischemic changes, development of pathological Q waves, imaging evidence of new loss of viable myocardium or new regional wall motion abnormality in a pattern consistent with an ischaemic etiology, evidence of an imbalance between myocardial oxygen supply and demand unrelated to acute athero-thrombosis.

8.1.3 Myocarditis

An acute myocarditis is defined as an event that meets the following criteria (49):

- a. Clinical presentations:
 - Acute chest pain, pericarditic, or pseudo-ischemic
 - New-onset (days up to 3 months) or worsening of: dyspnea at rest or exercise, and/or fatigue, with or without left and/or right heart failure signs
 - Subacute/chronic (3 months) or worsening of: dyspnea at rest or exercise, and/or fatigue, with or without left and/or right heart failure signs
 - Palpitation, and/or unexplained arrhythmia symptoms and/or syncope, and/or aborted sudden cardiac death
 - Unexplained cardiogenic shock
- b. Diagnostic criteria
 - ECG/Holter/stress test features:
 - Newly abnormal 12 lead ECG and/or Holter and/or stress testing, any of the following: I to III degree atrioventricular block, or bundle branch block, ST/T wave change (ST elevation or non ST elevation, T wave inversion), sinus arrest, ventricular tachycardia or fibrillation and asystole, atrial fibrillation, reduced R wave height, intraventricular conduction delay (widened QRS

- complex), abnormal Q waves, low voltage, frequent premature beats, supraventricular tachycardia
- Mycardiocytolysis markers Elevated TnT/TnI
 - Functional and structural abnormalities on cardiac imaging (echo/angio/CMR)
 - o New, otherwise unexplained LV and/or RV structure and function abnormality (including incidental finding in apparently asymptomatic subjects): regional wall motion or global systolic or diastolic function abnormality, with or without ventricular dilatation, with or without increased wall thickness, with or without pericardial effusion, with or without endocavitary thrombi
 - Tissue characterization by CMR (2018 Lake Louise criteria) (50):
 - o main criteria:
 - myocardial edema: T2 mapping or T2STIR
 - non-ischemic myocardial injury: abnormal T1, ECV (extracellular volume) or LGE (late-gadolinium enhancement)
 - o supportive criteria:
 - pericarditis: effusion in cine images or abnormal LGE, T2 or T1
 - systolic left ventricular dysfunction: regional or global wall motion abnormality

A myocarditis is clinically suspected in the presence of ≥ 1 clinical presentation and ≥ 1 diagnostic criterion from different categories, and in the absence of:

1. angiographically detectable coronary artery disease (coronary stenosis $\geq 50\%$);
2. known pre-existing cardiovascular disease or extra-cardiac causes that could explain the syndrome (e.g. valve disease, congenital heart disease, hyperthyroidism, etc.)

8.1.4 Stroke

Any stroke is defined as the presence of a new focal neurologic deficit thought to be vascular in origin, with signs or symptoms lasting more than 24 hours. It is strongly recommended (but not required) that an imaging procedure such as a Computerized Tomography (CT) or Magnetic Resonance Imaging (MRI) will be performed.

Both ischemic and hemorrhagic stroke will be considered as an endpoint and adjudication will have to differentiate the 2 types of events.

Diagnosis of stroke is based on clinical presentation (signs), duration and confirmatory investigations as follows:

- Clinical Presentation (At least 1 new neurological sign):

Hemiplegia, Hemianesthesia, Hemiparesis, Dysphasia, Vertigo, Diplopia, Dysphagia, Loss of vision on one side; Amaurosis fugax; Global amnesia; Bilateral or alternating weakness or sensory symptoms; Sensory loss; Dysarthria; Ataxia; Drop attacks; Another neurological sign

Duration (must be either ≥ 24 hours or ≤ 24 hours because of a pharmacologic or non-pharmacologic intervention).

- Confirmatory Investigations (At least 1):

Neurologist evaluation; Brain image study or procedure (CT-scan; MRI ± magnetic resonance angiography; Cerebral vessel angiography)

Stroke will be classified as follows:

1. **Transient ischemic attack**

TIA is defined as a transient episode of neurological dysfunction caused by focal brain, spinal cord, or retinal ischemia, without acute infarction

2. **Stroke**

Stroke is defined as an acute episode of neurological dysfunction caused by focal or global brain, spinal cord, or retinal vascular injury.

Classification:

A. Ischemic Stroke

Ischemic stroke is defined as an acute episode of focal cerebral, spinal, or retinal dysfunction caused by an infarction of central nervous system tissue. Hemorrhage may be a consequence of ischemic stroke. In this situation, the stroke is an ischemic stroke with hemorrhagic transformation and not a hemorrhagic stroke.

B. Hemorrhagic Stroke

Hemorrhagic stroke is defined as an acute episode of focal or global cerebral or spinal dysfunction caused by a nontraumatic intraparenchymal, intraventricular, or subarachnoid hemorrhage.

C. Undetermined Stroke

Undetermined stroke is defined as a stroke with insufficient information to allow categorization as A or B.

8.1.5 Heart failure

An episode of HF is defined as an event that meets the following criteria:

- a. for patients already discharged from the hospital: unplanned admission to an inpatient unit or an unplanned visit to the cardiologist or an emergency department

AND

- b. Clinical symptoms of heart failure, including at least one of the following new or worsening

- dyspnea
- orthopnea
- paroxysmal nocturnal dyspnea
- increasing fatigue/worsening exercise tolerance

AND

c. Physical signs of heart failure, including at least two of the following:

- edema (greater than 2+ lower extremity)
- pulmonary crackles greater than basilar (pulmonary edema must be sufficient to cause tachypnoea and distress not occurring in the context of an acute myocardial infarction or as the consequence of an arrhythmia occurring in the absence of worsening heart failure)
- jugular venous distension
- tachypnoea (respiratory rate > 20 breaths/minute)
- rapid weight gain
- S3 gallop
- increasing abdominal distension or ascites
- hepatojugular reflux
- radiological evidence of worsening heart failure
- A right heart catheterization within 24 hours of admission showing a pulmonary capillary wedge pressure (pulmonary artery occlusion pressure) ≥ 18 mm Hg or a cardiac output < 2.2 L/min/m²

NOTE:

Biomarker results (e.g., brain natriuretic peptide (BNP)) consistent with congestive heart failure will be supportive of this diagnosis, but the elevation in BNP cannot be due to other conditions such as cor pulmonale, pulmonary embolus, primary pulmonary hypertension, or congenital heart disease. Increasing levels of BNP, although not exceeding the ULN, may also be supportive of the diagnosis of congestive heart failure in selected cases (e.g. morbid obesity).

Echocardiographic abnormalities such as a reduction in LVEF $\geq 5\%$, increased left ventricular filling pressure or a dilated inferior vena cava should be documented (recommendation, not mandatory) to support the diagnosis of heart failure.

AND

d. Need for additional/increased therapy defined by:

- Initiation of, or an increase in, treatment directed at heart failure or occurring in a patient already receiving
- maximal therapy for heart failure and including at least one of the following:
 - Initiation of or a significant augmentation in oral therapy for the treatment of congestive heart failure
 - Initiation of intravenous diuretic, inotrope, or vasodilator therapy

- Up titration of intravenous therapy, if already on therapy
- Initiation of mechanical or surgical intervention (mechanical circulatory support, heart transplantation or ventricular pacing to improve cardiac function), or the use of ultrafiltration, hemofiltration, or dialysis that is specifically directed at treatment of heart failure.

AND

- e. No other non-cardiac etiology (such as chronic obstructive pulmonary disease, hepatic cirrhosis, acute renal failure, or venous insufficiency) and no other cardiac etiology (such as pulmonary embolus, cor pulmonale, primary pulmonary hypertension, or congenital heart disease) for signs or symptoms is identified.

NOTE: It is recognized that some patients may have multiple simultaneous disease processes. Nevertheless, for the end point event of heart failure requiring hospitalization, the diagnosis of congestive heart failure would need to be the primary disease process accounting for the above signs and symptoms.

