- ACE inhibitors primarily target ACE which has 42% sequence identity with ACE2 and may be effective on ACE2 as well. They may indirectly alter conformation of the receptor binding domain (RBD) binding site and affect the interaction of ACE2 with SARS-CoV-2 (41).
- RAS blockers have also demonstrated benefits in individuals developing cardiac injury and myocarditis, which is a frequent complication of COVID-19 (6,7).
- Eventually, it is well described that the discontinuation of RAS blockers in clinically stable individuals with cardiovascular disease or hypertension is associated with an increased risk of major cardiac events, especially hospitalization for acute heart failure, recurrent myocardial infarctions or stroke (42–44). As a result, the discontinuation of RAS blockers in infected patients with cardiovascular disease could make them more vulnerable to a severe form of COVID-19.

2.4 Description of the population to be studied and justification for the choice of participants

The population of the study will be formed by adult patients with diagnosis of COVID-19 requiring hospitalization and on prior therapy with RAS blockers with a duration ≥ 1 month.

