- Symptoms compatible with SARS-CoV-2 infection: fever, cough, dyspnea, anosmia, ageusia, ocular congestion, myalgia, sputum production, anorexia, fatigue, headache, sore throat, rhinorrhea, digestive symptoms (diarrhea, nausea, vomiting)
- Complete physical examination
- Biology: complete blood count, creatinine, blood urea nitrogen, potassium, sodium, bicarbonate, alanine/aspartate aminotransferase, bilirubin, albumin, lactate dehydrogenase, prothrombin time, activated partial thromboplastin time, D-dimers, troponin I us, creatine kinase, natriuretic peptides (BNP or Nt-proBNP), C-reactive protein, procalcitonin, ferritin, arterial blood gas with lactate
- Blood group and rhesus will be determined at inclusion if not performed earlier. Data will be collected in the CRF. Indeed, it has been reported in 2,173 Chinese patients with COVID-19 that blood group A was associated with a higher risk for acquiring COVID-19 compared with non-A blood groups, whereas blood group O was associated with a lower risk for the infection compared with non-O blood groups. this observation was reported in a preprint article without peer-review and further investigation are of the relationship between the ABO blood group and the COVID-19

susceptibility is important (Zhao J, Yang Y, Huang H, Li D, Gu D, Lu X, et al. Relationship between the ABO Blood Group and the COVID-19 Susceptibility. medRxiv. 27 mars 2020;2020.03.11.20031096.)

Any arterial puncture for collecting arterial blood gas and/or lactate should be performed after topical anesthesia with lidocaine 5% cream (EMLA)™

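### Criterion e of the heart-failure definition and its NOTE set different tests, and neither says how COVID-19 is handled for events during the index stay

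*Protocol*

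**What the plan says.** MACE at day 28 (cardiovascular death, myocardial infarction, stroke or acute heart failure) is the primary safety endpoint (Protocol 3.2, 4.1.2). Section 10.1 says the only identified potential risks are those of withdrawing RAS blockers, and that this endpoint evaluates them.

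Section 8.1.5 defines heart failure by criteria a to e, all joined by AND. Criterion a (an unplanned admission or visit) applies only to patients already discharged. Criterion b needs a new or worsening symptom, criterion c at least two signs, and criterion d added or increased therapy. Criterion e is the exclusion: "No other non-cardiac etiology (such as chronic obstructive pulmonary disease, hepatic cirrhosis, acute renal failure, or venous insufficiency", followed by a list of other cardiac causes, "for signs or symptoms is identified".

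The NOTE under e reads differently. It accepts that a patient may have several diseases at once. Its own test, which it words for heart failure that leads to admission, is that "the diagnosis of congestive heart failure would need to be the primary disease process accounting for the above signs and symptoms".

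Inclusion criteria 3 and 4 (6.1) require confirmed COVID-19 and hospitalization. The baseline visit (5.1) records "Symptoms compatible with SARS-CoV-2 infection: fever, cough, dyspnea" and, further down the same list, fatigue.

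**The concern.** Criterion e asks that no other cause be identified. The NOTE asks that heart failure be the main cause among possibly several. These tests give different answers when two processes contribute to the same picture, and in this trial a second process is present in every patient at entry. The NOTE might be taken to govern, but its wording fits a patient admitted because of heart failure, not one who decompensates while already in hospital for COVID-19.

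At stake is the endpoint on which the protocol relies to judge the safety of withdrawal. If a site applies e literally, genuine in-hospital heart failure may not be counted, and a reassuring MACE comparison could owe something to the definition. If sites differ in which test they apply, the endpoint is not the same across the trial.

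**Working it through.** No figure in the protocol bears on this point: it gives no heart-failure rate, no MACE rate and no power for MACE. The check is therefore a comparison of the text, followed by an illustration on assumed rates.

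**1. In-hospital events are meant to count.** Criterion a is limited to discharged patients, and section 5.2 records heart failure, congestive signs and IV diuretics daily during the stay.

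**2. The overlap is with listed items.** Sections 2.2 and 5.1 both give dyspnea and fatigue as COVID-19 symptoms, and both appear in criterion b. Tachypnoea and crackles in criterion c can also come from pneumonia. Jugular distension, S3 gallop, hepatojugular reflux and raised wedge pressure, also in c, point to congestion.

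**3. One patient, two tests.** Take an inpatient with COVID-19 pneumonia whose dyspnea worsens, who develops jugular distension and tachypnoea, and who is started on an IV diuretic. Criteria b, c and d are met, and a does not apply.
- Under e read literally, pneumonia is an identified non-cardiac cause of the dyspnea and tachypnoea: not an event.
- Under the NOTE, if heart failure is judged the primary process: an event.

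The text does not say which answer governs.

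**4. The protocol handles attribution differently elsewhere.** The ARDS definition (8.1.7) asks that respiratory failure be not fully explained by cardiac failure or fluid overload, which allows coexisting causes. The expedited-notification list (10.3.2.2.1) qualifies acute heart failure as not related to COVID-19. Section 8.1.5 does neither.

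**5. Who decides.** The trial is open label (4.2.1). Section 9 describes only a steering committee, and adjudication is mentioned in 8.1.4 for stroke type. For heart failure the protocol does not say who makes the attribution or whether that person is masked.

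**6. Direction.** Section 2.3 suggests that continuing RAS blockers could enhance acute kidney injury, while 2.7 lists more acute lung injury as a risk of discontinuation. The competing explanations may thus differ by arm, so the bias need not run only toward no difference.

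**7. Illustration.** From the protocol: 277 per arm (4.2.2) and a comparison of proportions (12.5). Assumed: a two-sided 5% test, other MACE of 3% in both arms, true heart failure of 3% (continuation) vs 8% (discontinuation), and the same share f of heart-failure events dropped in both arms.

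MACE rate = 3% + (1 − f) × HF rate. Power ≈ Φ[(Δ − 1.96·SE₀)/SE₁], where SE₀ is the pooled and SE₁ the unpooled standard error.

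For f = 0: SE₀ = √(2 × 0.085 × 0.915/277) = 0.0237; SE₁ = √((0.06 × 0.94 + 0.11 × 0.89)/277) = 0.0236; (0.05 − 0.0464)/0.0236 = 0.15; power 0.56.

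| Share dropped | MACE, continuation vs discontinuation | Difference | Power |
|---|---|---|---|
| 0% | 6.0% vs 11.0% | 5.0 points | 56% |
| 30% | 5.1% vs 8.6% | 3.5 points | 37% |
| 50% | 4.5% vs 7.0% | 2.5 points | 24% |
| 80% | 3.6% vs 4.6% | 1.0 point | 9% |

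Other assumed rates, all with half the heart-failure events lost:
- Other MACE 4%, HF 5% vs 15%: 93% falls to 54%.
- Other MACE 4%, HF 5% vs 10%: 45% falls to 20%.
- Other MACE 8%, HF 5% vs 10%: 37% falls to 15%.

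The table shows what a given loss would cost. It is no evidence that such a loss would occur.

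**The case against.** The strongest reply is that a sensible clinician would have little trouble. Criterion e asks what caused the signs, not whether another disease is present. COPD is on the same list, and nobody would read e as barring every COPD patient from a heart-failure event. Symptoms must be new or worsening, and several signs in c are not explained by COVID-19. The NOTE expressly accepts coexisting disease. The signal is not lost to the trial either: adverse events are recorded in the CRF, serious events go to the DSMB before its meetings, and all are tabulated by arm (10.3.2, 12.5).

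Most of this stands, and it limits the point. A reader might infer that e rules out every in-hospital event because all participants have COVID-19, or that concurrent acute kidney injury disqualifies automatically. The documents do not support either reading: e concerns causes of signs or symptoms, and the NOTE allows simultaneous processes. A reader might also take heart failure to be the component most expected to rise. Section 2.3 says "especially hospitalization for acute heart failure, recurrent myocardial infarctions or stroke", which lists it first but does not rank it above the others.

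The reply does not remove the conflict between e and the NOTE, the NOTE's uncertain reach for patients already in hospital, or the silence on COVID-19. Adverse-event tables are a useful backstop but are not the designated primary safety endpoint. It is also fair that e guards against the opposite error: pneumonia alone can supply dyspnea, tachypnoea and crackles, so deleting e would invite over-counting.

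**Conclusion.** The point holds as a defect in an endpoint definition. Criterion e and its NOTE set two tests that can classify the same in-hospital patient differently. Neither addresses the disease every participant has, and the stricter one, read literally, can drop genuine heart failure from the primary safety endpoint. With open treatment and no stated masking of this judgement, the choice of test may be made by someone who knows the arm.

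The size is unknown. The protocol supplies neither event rates nor anything from which to estimate the share of events e would exclude, so the power figures rest wholly on assumptions. In the first scenario power is only 56% even with every event counted, so limited power for MACE is not caused by e. It is worth correcting because the change is cheap and the endpoint carries the safety conclusion.

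**What to change.** Replace criterion e and its NOTE with one test, stated to apply both to index-stay events and to events after discharge. One form is that the signs and symptoms are not fully explained by another etiology, as in the ARDS definition in 8.1.7. Add that coexisting COVID-19 or acute kidney injury does not by itself exclude an event that otherwise meets b to d with signs of congestion. This keeps the guard against counting pneumonia as heart failure.

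Keep natriuretic peptide, echocardiographic and radiological findings as supportive, not required. Peptides are listed at inclusion, but later biology is at the physician's decision (5.2), and imaging is done if indicated (5.6). Making the endpoint depend on discretionary tests in an open-label trial could tie event detection to the arm.

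Add a CRF item recording when e is the reason an event is not counted, and report MACE under the current strict wording as a sensitivity analysis. The item also measures the under-count that cannot be estimated now.

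The cost is an amendment to the endpoint wording, one CRF field and one extra analysis. The downside is that some COVID-related congestion may be counted as heart failure in both arms. The change does not mask the attribution, which remains a consequence of the open-label design.

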8.1.6 Acute kidney injury

Acute kidney injury is defined by the KDIGO Guidelines as follows (45):

- increase in serum creatinine $\geq 26.5 \mu\text{mol/L}$ within 48h
- or increase in serum creatinine ≥ 1.5 times baseline within the last 7 days
- or urine output $< 0,5 \text{ ml/kg/h}$ for 6 hours

Its severity is staged according to the following criteria:

- stage 1:
 - increase in serum creatinine $\geq 26.5 \mu\text{mol/L}$ within 48h
 - or increase in serum creatinine ≥ 1.5 times baseline within the last 7 days
 - or urine output $< 0.5 \text{ ml/kg/h}$ for 6 hours
- stage 2:
 - increase in serum creatinine 2-2.9 times baseline
 - or urine output $< 0.5 \text{ ml/kg/h}$ for ≥ 12 hours
- stage 3:
 - increase in serum creatinine $\geq 353.6 \mu\text{mol/L}$
 - or increase in serum creatinine ≥ 3 times baseline
 - or initiation of renal replacement therapy
 - or urine output $< 0.3 \text{ ml/kg/h}$ for ≥ 24 hours
 - or anuria ≥ 12 hours

